### **8.3 Statistical criteria of termination of trial**

Interim analyses will be considered, to be able to terminate the study in advance if significance is found. In particular, when 38 patients (40% of the sample size) and 57 patients (60% of the sample size) are reached, the significance will be tested. If significance is found, the trial can be terminated with the patients already collected.

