## 8. STATISTICAL METHODS

### 8.1 Hypothesis

This study is designed to test the null hypothesis that the proportion of 'event' (intended as procedure incomplete or serious adverse event) is equal or greater than 20%. The alternative hypothesis is that the proportion of 'event' is less than 20%. In statistical terms:

$$H0: p \geq 20\%$$

$$H1: p < 20\%$$

Where:

$p$  = true proportion of patients with event

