### 8.2 Determination of Sample Size

Efficacy (first primary objective) will be assessed by measuring the colonoscopy completion rate in long-lasting procedures, which is a measurable parameter of clinical value recognized by international medical societies. Safety (second primary objective) will be assessed by measuring the rare of adverse events. They are classified into: serious gastrointestinal events; myocardial infarction; stroke; pneumonia. Based on the literature [30]; their occurrence rates in screening or surveillance colonoscopy are 47 persons, 4 persons, 7 persons and 10 persons per 100'000, respectively.

These two objectives are merged in one indicator, which is equal to 1 for each subject if the procedure is incomplete or an adverse event occurs, and 0 otherwise.

The non-completion rate of long-lasting colonoscopies conducted with Endorail is expected to be around 10%. This will be compared to the above-mentioned threshold of 20% for incomplete procedures. It should be noted that this threshold is conservative and represents the most critical setting for comparison with respect to the state of the art, as it is derived from the lower bound of the range from the literature.

When including the safety to provide the expected value of the indicator for Endorail and the corresponding threshold, the above values of 10% minimally change, as the adverse event

occurrence rate is 0.068% (given by the sum of the occurrence of the 4 events reported above per 100'000 persons, expressed in percentage).

With a significance level  $\alpha$  of 5%, assuming a proportion of outcome of 10.1%, 85 patients allow to test with a power of 80% the  $H_0: p \geq 20\%$  vs  $H_1: p < 20\%$ , where 20% is the estimated percentage of incomplete procedure from literature.

The chosen number is then increased by the 10% to account for possible drop-out (e.g., cases to be discarded, losses to follow-up, etc.), resulting in  $85/0.90 = 95$  patients to be actually enrolled.

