### **8.4 Planned Analyses**

The statistical analysis plan will be finalized before Data Base Lock and it will include a more technical and detailed description of the statistical analyses described in this section. This section is a summary of the planned statistical analyses.

All data obtained in this study and documented in the eCRFs will be listed and summarized as appropriate:

- for quantitative variables: standard quantitative statistics (N, mean, standard deviation, median, interquartile range, minimum and maximum);
- for qualitative variables: frequency distribution [number of non-missing observations (N) and percentages (%)].

A statistical test will be performed to assess the significant difference of the indicator with respect to the threshold and statistically prove efficacy of Endorail in long-lasting procedures. Due to the type of variable, the exact binomial test will be adopted. Additionally, considering as alternative hypothesis that the rate observed in the analyzed population is less than the respective threshold, the one-tailed test will be adopted.

Medical adverse events and medical device adverse events will be collected during the study.

The number of adverse events (AEs) – related or not to the medical device – and the number and proportion of patients with at least one AE will be presented.

All adverse events will be tabulated by System Organ Class (SOC) and Preferred Term (PT) after medical coding using the Medical Dictionary for Regulatory Activities (MedDRA) thesaurus version 24.1. The primary SOC and the PT will be used for the analysis of the frequency

distribution.

The frequency of occurrence of specific adverse events (gastrointestinal bleedings, intestinal perforation, mucosal petechiae, abdominal pain) will be presented by means of default descriptive statistics.

Statistical analyses will be carried out using R Statistical Software (Foundation for Statistical Computing, Vienna, Austria).

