#### **8.4.2 Interim analyses**

Two interim analyses will be planned, a first when 40% of the sample size (38 patients) is reached and a second when 60% of the sample size (57 patients) is reached. During these interim analyses the significance will be tested. If significance is found, the trial can be terminated with the patients already collected.

38 patients guarantee a statistical power of 80% if at least 93.9% of these are free of 'event' (intended as procedure incomplete or serious adverse event). 57 patients guarantee a statistical power of 80% if at least 91.8% of these are free of 'event'.

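### Testing at 38 patients, 57 patients and the end, each at the full one-sided 5%, gives a false-positive rate of about 8%, not the stated 5%

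*Combined protocol and SAP*

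**What the plan says.** Section 8.1 sets the null hypothesis that the proportion with an event "is equal or greater than 20%. The alternative hypothesis is that the proportion of 'event' is less than 20"%. Section 8.4 specifies the test: "Due to the type of variable, the exact binomial test will be adopted", and "the one-tailed test will be adopted".

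Section 8.2 gives the only significance level in the plan: a level "of 5%, assuming a proportion of outcome of 10.1%, 85 patients allow to test with a power of 80"%. Allowing 10% for drop-out turns 85 into 95 enrolled.

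Section 8.3 adds two interim looks: "when 38 patients (40% of the sample size) and 57 patients (60% of the sample size) are reached, the significance will be tested". Section 8.4.2 states the consequence: "If significance is found, the trial can be terminated with the patients already collected". Section 4.6 repeats the same rule. Section 8.4.2 also gives power figures for the looks, for example "38 patients guarantee a statistical power of 80% if at least 93.9% of these are free" of an event. The matching figure for 57 patients is 91.8%.

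No section gives an alpha-spending function, an interim boundary, a reduced level or a multiplicity statement. Section 8.4 leaves technical detail to a statistical analysis plan that has to be final only before database lock.

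**The concern.** The rule gives three chances to declare success and does not say how the 5% is shared among them. If each look uses the full 5%, the overall chance of a false success must exceed the level of any single look.

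This is the trial's only confirmatory test, in an open-label single-arm study judged against a literature threshold, so the error rate attached to it carries the efficacy claim. The interim looks are also likely to decide the trial. At the planning rate of 10.1%, the chance of crossing is 46% at 38 patients and 68% by 57.

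Stopping at 38 would also leave little evidence for the co-primary safety objective. With no device-related serious event in 38 patients, the one-sided 95% upper limit is still 1 − 0.05^(1/38) = 7.6%.

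**Working it through.** **Inputs.** Null rate p0 = 20% (8.1); planning rate p1 = 10.1%, level 5%, power 80%, 85 evaluable and 95 enrolled (8.2); looks at 38 and 57 (8.3); exact binomial, one-tailed (8.4); interim power figures of 93.9% and 91.8% event-free (8.4.2).

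**1. Reproduce the sample size.** One-sided normal approximation:

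n = [(z₀.₉₅√(p0·q0) + z₀.₈₀√(p1·q1)) / (p0 − p1)]²
= [(1.645 × 0.4 + 0.842 × 0.3013) / 0.099]² = 84.8, so 85. Then 85/0.90 = 94.4, so 95. Both match the plan.

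**2. Find the level used at each look.** Solve the same formula for the event rate p that gives 80% power at a fixed n:

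(0.20 − p)√n = 1.645 × 0.4 + 0.842√(p(1 − p))

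| Level per look | n = 38, event-free | n = 57, event-free |
|---|---|---|
| 5% | 93.9% | 91.8% |
| 4.5% | 94.2% | 92.0% |
| 2.5% | 95.5% | 93.2% |
| Plan, 8.4.2 | 93.9% | 91.8% |

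Of these levels, only the full 5% returns both printed figures. With the planned exact test at 5%, power at those rates is 80.0% (n = 38) and 81.6% (n = 57). At 2.5% it would be 58.9% and 67.6%.

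**3. Rejection limits.** At each look, take the largest x with P(X ≤ x | n, 0.20) ≤ 5%.

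| n | Reject if events ≤ | Level of that look alone |
|---|---|---|
| 38 | 3 | 3.87% |
| 57 | 6 | 4.51% |
| 85 | 10 | 3.32% |
| 95 | 12 | 4.24% |

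**4. Overall error.** Start from the binomial distribution at n = 38, remove the outcomes that have already crossed, convolve with the next group of patients, and repeat. This gives the probability of first crossing at each look.

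| True rate | Final n | Look 1 | Look 2 | Final | Total |
|---|---|---|---|---|---|
| 20% | 85 | 3.87% | 2.46% | 1.26% | **7.59%** |
| 20% | 95 | 3.87% | 2.46% | 2.06% | **8.39%** |
| 10.1% | 85 | 45.7% | 22.2% | 13.4% | 81.3% |
| 10.1% | 95 | 45.7% | 22.2% | 19.1% | 86.9% |

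The two interims together give 3.87% + 2.46% = 6.33%, so 5% is passed before the final analysis. For any final n from 85 to 95 the total lies between 7.3% and 8.7%. These totals already include the conservatism of the exact test; a normal approximation that ignores discreteness gives 9.5% to 9.8%.

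**5. A boundary that holds 5%.** O'Brien-Fleming-type spending of 5% at fractions 0.4, 0.6 and 1 allows cumulative error of 0.19%, 1.14% and 5%. In exact binomial terms:

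| Limits (events ≤) | Looks | Overall alpha | Power at 10.1% |
|---|---|---|---|
| 0 / 4 / 12 | 38 / 57 / 95 | 4.4% | 84.2% |
| 0 / 4 / 10 | 38 / 57 / 85 | 3.5% | 76.6% |
| 1 / 4 / 12 (classical O'Brien-Fleming) | 38 / 57 / 95 | 4.5% | 84.2% |
| 2 / 5 / 11 (Pocock-type) | 38 / 57 / 95 | 3.8% | 77.6% |

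**The case against.** - **The plan never says in words that each look uses 5%, and the later analysis plan could set a boundary.** The first part is true. But the printed interim figures come from a 5% level, and the text deferring to the analysis plan does not mention alpha control. That document is due only before database lock, so both looks at open-label outcomes could come first.

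- **The exact test cannot identify the level.** This stands as a point of method. The limit of 3 in 38 holds for any level from 3.87% to just under 9.86%, and 6 in 57 for any level from 4.51% to just under 9.34%. The inference to 5% rests on the normal approximation in step 2, which is also the formula behind the plan's 85.

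- **The efficacy endpoint is also worded as an incompletion rate of 10% or less.** If success also required an observed indicator rate of at most 10%, the limits would be 3/38, 5/57 and 8/85 (or 9/95), and the overall error 4.7% (or 4.6%). But the stopping rule in 4.6, 8.3 and 8.4.2 refers only to significance. The 8% is therefore the error of the significance test as written.

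- **Stopping is optional.** Also true. The figures assume success is claimed at the first significant look. An option to claim success still has to be counted in the error rate.

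- **Correcting the boundary costs power.** With only 85 analysed, power under the 0/4/10 limits is 76.6%, against 81.3% for the uncorrected rule. Most of the shortfall below 80% does not come from the correction: a single exact test at 85 has 76.3% power, because 85 was derived from the normal approximation.

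**Conclusion.** The concern holds. The stated 5% is not the error rate of the rule as written. That rate is 7.6% with 85 patients at the end and 8.4% with 95, or about 1.5 to 1.7 times the claim.

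This rests on three assumptions: the full one-sided 5% at each look, as the plan's interim figures indicate; success declared at the first significant look; and looks at exactly 38 and 57 patients. It must be settled before the first interim, because a boundary chosen after open-label results have been seen would not be credible.

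**What to change.** State in sections 4.6, 8.3 and 8.4.2 a group-sequential boundary with overall one-sided alpha of at most 5%, given as event counts. One workable choice is to stop for success only at 0 events in 38 or at most 4 in 57, and otherwise declare success at 12 or fewer in 95. Other boundaries, such as 1/4/12, also serve. What matters is that one is fixed in advance. Replace the 93.9% and 91.8% statements in 8.4.2 with the chosen limits, say how the final limit is recalculated if fewer than 95 are analysed, and require the analysis plan to be final before the first look.

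The cost is wording only. No patients are added, and the final limit at 95 stays at 12. Early stopping becomes less likely: under 0/4/12 at a 10.1% event rate, the chance of stopping is 1.7% at 38 and 1.7% + 28.8% = 30.6% (from unrounded values) by 57, against 46% and 68% now. The 84.2% power needs all 95 patients in the analysis; at 85 it is 76.6%, which the sponsor should weigh when confirming the sample size.

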### **8.4 Planned Analyses**

The statistical analysis plan will be finalized before Data Base Lock and it will include a more technical and detailed description of the statistical analyses described in this section. This section is a summary of the planned statistical analyses.

All data obtained in this study and documented in the eCRFs will be listed and summarized as appropriate:

- for quantitative variables: standard quantitative statistics (N, mean, standard deviation, median, interquartile range, minimum and maximum);
- for qualitative variables: frequency distribution [number of non-missing observations (N) and percentages (%)].

A statistical test will be performed to assess the significant difference of the indicator with respect to the threshold and statistically prove efficacy of Endorail in long-lasting procedures. Due to the type of variable, the exact binomial test will be adopted. Additionally, considering as alternative hypothesis that the rate observed in the analyzed population is less than the respective threshold, the one-tailed test will be adopted.

Medical adverse events and medical device adverse events will be collected during the study.

The number of adverse events (AEs) – related or not to the medical device – and the number and proportion of patients with at least one AE will be presented.

All adverse events will be tabulated by System Organ Class (SOC) and Preferred Term (PT) after medical coding using the Medical Dictionary for Regulatory Activities (MedDRA) thesaurus version 24.1. The primary SOC and the PT will be used for the analysis of the frequency

distribution.

The frequency of occurrence of specific adverse events (gastrointestinal bleedings, intestinal perforation, mucosal petechiae, abdominal pain) will be presented by means of default descriptive statistics.

Statistical analyses will be carried out using R Statistical Software (Foundation for Statistical Computing, Vienna, Austria).

#### **8.4.1 Datasets to be analysed, analysis populations**

- Screening set: will include all patients who have signed the informed consent and have been screened for inclusion in the study;
- Intention-to-treat population (ITT): will include all enrolled patients who have started treatment with Endorail;
- Per-Protocol (PP) population: will include all patients of the ITT who also meet all inclusion/exclusion criteria and who do not have any major protocol deviation, to be defined in a data review meeting (DRM) of the Sponsor, Contract research Organization (CRO) representatives and the biostatistician.

Analysis will be performed on the ITT population and will be repeated in the PP population. The results obtained in the PP population will be seen as confirmative of those observed in the ITT population.

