## 1.4 Clinical Evidence to Date

With the intent of providing clinical evidence to further support the safety and efficacy profile of the Endorail, a First-In-Man (FIM) clinical trial has been conducted. This study, named "ESPILOT2019H", was initiated on February 11, 2020, and required the enrolment of a total of 25 evaluable Italian patients undergoing elective colonoscopy. Following the enrolment of the first six (6) patients however, the particularly severe COVID-19 outbreak experienced in Italy forced an early interruption of the study recruitment by the affected medical centers. Given the great uncertainty about a realistic timeline for a possible study resumption, Endostart decided to terminate the trial on March 11, 2020. This decision was not due to the occurrence of any adverse events, or safety concerns, or other device-related reasons.

All 6 patients completed the colonoscopy in the expected timeframe without any adverse event or complications. Five (5) of the six (6) enrolled patients completed the study according to the protocol. In the very first patient however, due to an error of the device technical information

sheet, a pediatric colonoscope was utilized with a tool channel diameter smaller than required (3.2 mm instead of 3.7 mm), which did not allow the successful insertion of the Endorail Balloon Guide. For this one patient, the colonoscopy was continued and completed in the traditional manner without the use of the subject device.

Following a protocol amendment, whereby the reference colonoscope channel diameter to be used was specified to be  $\geq 3.7$  mm, all loops formed in the other 5 patients were successfully resolved with the Endorail.

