### Exclusion Criteria

1. Body mass index (BMI) > 30 kg/m^2;
2. Outpatients undergoing colonoscopy for colorectal cancer screening or therapeutic indication;
3. Patients in class >2 physical status of the classification system of American Society of Anaesthesiologists;
4. Any contraindications to colonoscopy;
5. Any contraindications to sedation;
6. Known allergy or hypersensitivity to any of the elements of the Endorail Set (e.g.: iron);
7. Patients with permanently or semi-permanently implanted medical devices, (e.g. orthopedic implants, trauma fixation devices, cardiac pacemakers, implantable cardioverter defibrillator, drug pumps, neurostimulators, vascular stents, cochlear implants, aneurysm clip);
8. Presence of dense diverticulosis
9. Presence of diverticulitis
10. Presence of ferromagnetic foreign body;
11. Presence of large abdominal hernias;
12. Urgent colonoscopy;
13. Presence of severe thrombocytopenia;
14. Presence of severe granulocytopenia;
15. Presence of severe coagulopathy;
16. Presence of peritonitis;
17. Presence of colonic wall ischemia or necrosis or injured mucosa; ;
18. Presence of peritoneal carcinomatosis;
19. Boston Bowel Preparation Scale <2 in at least one of the colonic segments;
20. Presence of obstructing masses and strictures of the colon;
21. History of total or subtotal colectomy.
22. Presence of angulated and fixed colon curves;
23. Pregnant or breast-feeding women;
24. Patient unable to provide the signed informed consent, uncooperative patient or patient unlikely to comply with the protocol or unable to understand the nature, scope and possible consequences of the study;
25. Presence of any other reason that, in the opinion of the investigator, prevents the subject from participating in the study or compromises the subject safety
26. Concomitant participation in other clinical investigations or participation in the evaluation of any investigational product/device in the 30 days before this study or previous participation in the same investigation;
27. Urgent colonoscopy.

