#### **4.4 Recruitment and screening**

Before starting the recruitment, each investigator must be familiar with the device under investigation.

If the Investigator has never used the Endorail device, he/she should perform at least three colonoscopy procedures with Endorail. To assess the performance case, the Investigator should sign a self-declaration titled “Performance case declaration” stating that the three cases have been duly performed in compliance with Protocol requirement.

Before any screening procedure all patients must sign a written informed consent for the study. The following logs must be maintained at each study site and kept in the Investigator Site File: a “Subject Screening Log\Enrolment Log”, to document the identification of subjects who enter screening and to document chronological enrolment of patients, a “Subject Identification List” for all subjects registered to maintain the correlation with the patient's full identification data (name, surname - confidential).

Eligible patients who have provided written informed consent to study participation and that satisfy all inclusion criteria and none of the exclusion criteria both detailed in Section 4.3, will be enrolled in the clinical study.

Eligibility will be determined by the investigator basing on standard colonoscopy clinical history and colonoscopy indication. Enrolment will be completed during colonoscopy if caecal intubation time is longer than 10 min.

When the investigator registers in the eCRF the enrolment of a new patient, the eCRF will assign a 4-digit identification number to each patient included in the investigation. The patient number will be sequentially assigned to each patient who signs the informed consent, starting from 0001. If a subject discontinues from the study, the patient number will not be re-used, and the subject will not be allowed to re-enter the study. Moreover, to distinguish the patient number of different sites involved in the clinical trial, the 4 digit patient number will be preceded by a 2-digit site number. Before the study initiation, the Sponsor will assign to each participating site its unique 2-digit site number.

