## **5.2 Experimental Intervention (treatment/medical device)**

Endorail is a colonoscopy add-on device developed to be used without any modification to colonoscopes. Endorail is an accessory to an endoscope and is intended to facilitate positioning of a standard colonoscope during endoscopy of the large intestine. Endorail works as a magnetic anchor that is able to guide the colonoscope and to straighten colon curves and loops.

**In case caecal intubation time is longer than 10 minutes**, the balloon is inserted in the endoscope tool channel, advanced beyond the colonoscope tip and filled with 25 mL of biocompatible Endorail Ferromagnetic Fluid. The operator manually performs and controls the inflation and deflation of the balloon through the syringe. Thus, by applying the Endorail Handpiece over the patient abdomen, the balloon can be magnetically anchored. The magnetic power level can be increased by the operator according to the patient's body mass index and the successful anchorage of the balloon can be visually verified by the operator through the endoscopic images.

For achieving the optimal effectiveness, anchorage should be performed in any colon segments proximal to the sigmoid colon (descending colon, transverse colon, ascending colon, caecum and colon curves).

The anchored balloon guide allows to straighten the scope and thus the colon itself. As the balloon guide is kept in tension, its rigidity increases and works as a rail supporting the movements of the colonoscope. The guided colonoscope can thus be easily moved back and forward to allow better colonoscope positioning and colonoscopy completion.

The Endorail Balloon Guide pulled against the colonic wall by the handpiece magnetic field works as a distal anchor towards which the endoscope tip is advanced and the Endorail Balloon Guide inflation tube serves as a guide wire that leads the endoscope as it is pushed towards the magnetically anchored balloon. After the Endorail is removed, the straightened colonoscope can be easily pushed forward to achieve colonoscopy completion as foreseen in standard endoscopic technique.

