#### 6.2.1 Treatment Visit - Visit 1 (Day 1)

Potential participant patients, prospectively attending the investigational study to undergo colonoscopy, will be informed, orally and in writing, about the scope of the study, the relevant procedures, the nature of the risks related to the study, and they will be asked to sign and date the written Informed Consent Form.

After the correct obtaining of the Informed Consent, the following assessments and procedures will be performed during Visit 1 (Day 1):

- Demographic data (age, sex, race) will be recorded;
- A detailed medical history, with special attention to previous history of diverticular disease, hysterectomy, gastrointestinal surgery, implantable devices will be recorded in the patient's medical record and in the appropriate section of the eCRF;
- All concomitant medications being taken by the patient, including treatments administered in the last 4 weeks, will be checked and will be recorded in the patient's medical records and in the appropriate section of the eCRF;
- A general physical examination will be performed. The physical examination will include an examination of head, ears, eyes, nose, mouth, skin, heart, and lung examinations, lymph nodes, genitourinary, gastrointestinal, skeletal, and neurological systems. Any identified abnormality should be recorded in the patient's medical records and in the eCRF;
- Height, weight, BMI;
- Vital signs (blood pressure, heart rate) will be measured and will be recorded both in the patient's medical record and in the appropriate section of the eCRF;
- Inclusion/exclusion criteria will be reviewed and eligible patients will be included in the study;
- Pre-procedure sedation will be performed according to the standard of care;
- Procedure for colonoscopy will be started;
- Caecal intubation time will be recorded;
- Colonoscopy will be performed and completed according to procedures detailed in Section 5.2.;
- In case caecal intubation time is longer than 10 minutes, the patients can be enrolled.
- The occurrence of local (intra-procedure) adverse events (i.e. gastrointestinal bleeding, intestinal perforation, presence of mucosal petechiae and abdominal pain) will be checked and (if any) will be recorded in the patient's medical records and in the appropriate section of the eCRF;
- At the end of the colonoscopy, successful or failed caecal intubation will be recorded in the patient's medical record and in the appropriate section of the eCRF;

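### The set labelled ITT counts only enrolled patients in whom Endorail was started, while the 20% threshold covers all long-lasting colonoscopies, and no efficacy analysis shows the cases in between.

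*Combined protocol and SAP*

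**What the plan says.** Section 8.4.1 defines the ITT population: it "will include all enrolled patients who have started treatment with Endorail". PP is drawn from ITT by removing patients with eligibility failures or major deviations. On the use of the two sets, "Analysis will be performed on the ITT population and will be repeated in the PP population". A screening set of all consented patients is defined, but no efficacy analysis is attached to it.

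On enrolment, section 4.4 says: "Enrolment will be completed during colonoscopy if caecal intubation time is longer than 10 min". Section 6.2.1 is looser: "In case caecal intubation time is longer than 10 minutes, the patients can be enrolled". Section 4.4 bases eligibility on clinical history and indication, and 6.2.1 lists the criteria review before the colonoscopy starts. Some exclusions in 4.3 may nevertheless first be recognised with the scope in place: "Presence of angulated and fixed colon curves" (item 22), "Presence of obstructing masses and strictures of the colon" (item 20), dense diverticulosis (item 8), a low bowel preparation score (item 19) and the investigator-opinion criterion (item 25).

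Section 1.2.3 derives the threshold. About 20% of colonoscopies last over 10 minutes, nearly all incomplete procedures fall in that group, and the lower-bound overall incompletion rate of 4% is multiplied by five to give 20%. No eligibility or device-suitability filter is applied.

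**The concern.** A single-arm trial with no concurrent control depends on its own denominator matching that of the external rate. Here the external denominator is all long-lasting cases, and the trial's denominator is long-lasting cases that were enrolled and in which the device was started. The step between them comes after the operator has watched ten minutes of a difficult insertion.

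Several of the exclusions that may surface then plausibly make completion harder. If the cases leaving at that point fail more often than the rest, the analysed rate drops below 20% even with an inert device. The PP analysis cannot reveal this, because it lies inside the same set. The plan also does not define what counts as starting treatment, so it is unclear where a case with a failed balloon insertion belongs.

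**Working it through.** **Inputs from the plan.** Threshold 20% (1.2.3, 8.2); expected rate 10.1%, one-sided 5%, 80% power, 85 evaluable and 95 enrolled (8.2); exact binomial one-tailed test (8.4).

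**Plan's own figures.**
- Threshold: 0.04 / 0.20 = 20%, with all long-lasting cases as the denominator.
- Sample size, normal approximation: n = [1.645·√(0.20·0.80) + 0.842·√(0.101·0.899)]² / (0.20 − 0.101)² = 84.8, so 85; 85/0.90 = 94.4, so 95. Both reproduce.
- Exact test at n=85: P(X≤10 | 0.20) = 3.3% and P(X≤11 | 0.20) = 6.3%, so success needs 10 events or fewer. Power at 10.1% is 76.3%.
- Exact test at n=95: success needs 12 events or fewer, error 4.2%, power 84.0%.

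**Effect of selection.** Let d be the share of long-lasting cases that never enter the analysed set and f the incompletion rate among them. Neither is in the documents; both are assumptions. With an inert device and a true rate of 20%, the analysed rate is r = (0.20 − d·f)/(1 − d), and false success is P(X≤10 | 85, r) or P(X≤12 | 95, r).

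| d | f | r | n=85 | n=95 |
|---|---|---|---|---|
| any | 20% | 20.0% | 3.32% | 4.24% |
| 2% | 40% | 19.6% | 4.04% | 5.17% |
| 2% | 50% | 19.4% | 4.45% | 5.70% |
| 5% | 40% | 18.9% | 5.46% | 7.00% |
| 5% | 50% | 18.4% | 6.90% | 8.86% |
| 10% | 60% | 15.6% | 21.1% | 26.6% |

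Example for d=5%, f=50%: (0.20 − 0.025)/0.95 = 0.184. The first row shows that there is no bias when the missing cases fail at the common rate.

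**If the true rate is above 20%.** Assume 25%. With d=5%, f=50%, r = (0.25 − 0.025)/0.95 = 23.7% and false success at n=85 is 0.45%. With d=10%, f=60%, r = (0.25 − 0.06)/0.90 = 21.1% and false success is 1.9%. Both are below 3.3%.

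**Sensitivity to one case.** 10/85 gives p=0.033; adding one untreated incomplete case gives 11/86, p=0.057. Likewise 12/95 (p=0.042) becomes 13/96 (p=0.068).

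**Price of making every long-lasting case primary.** With 10.1% in treated cases, the overall rate is (1 − d)·0.101 + d·f. For d=5%, f=40% this is 0.096 + 0.020 = 11.6%, and power at n=85 falls from 76% to 60%. For d=10%, f=60% it is 15.1%, and power is 25%.

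These figures ignore the two interim looks and the 0.068% adverse-event contribution to the indicator.

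**The case against.** The strongest reply is that the protocol does not leave enrolment to choice. Section 4.4 says eligible consented patients will be enrolled, 4.1 says they will take part, and the synopsis and sections 5.2 and 5.3.1 describe Endorail as used once 10 minutes have passed. Skipping an eligible case would depart from the protocol. This stands. A reader might infer from the permissive wording in 6.2.1 that hard cases can be dropped freely, but the other sections do not support that. What remains is exclusions recognised during insertion, and enrolled patients in whom the device is not started.

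A reader might also take the first-in-man case, in 1 of 6 patients, as a guide to how often starts fail. Section 1.4 reports a narrow tool channel, "which did not allow the successful insertion of the Endorail Balloon Guide". The cause was an error in the technical sheet, section 5.2.1 now requires at least 3.7 mm, and that colonoscopy was completed. Dropping a completed case raises the incompletion rate. The episode shows only that a non-start can happen.

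Nor does section 5.2 say that cases stuck in the sigmoid are where the device works least well. It says that, for best effect, "anchorage should be performed in any colon segments proximal to the sigmoid colon". That concerns where the balloon is anchored, and the balloon is advanced beyond the scope tip.

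Finally, section 8.2 calls 20% conservative. That may offset the bias, as the 25% example shows, but it does not make the denominators agree. The screening log and the promised data listings help, yet no caecal outcome is explicitly planned for untreated long-lasting cases.

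**Conclusion.** The concern holds as a gap in the analysis sets and should be closed. The confirmatory set is narrower than the population behind the threshold, part of the narrowing can follow observed difficulty, and no planned efficacy analysis would show it.

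The size cannot be fixed from the documents. Under the modest assumptions above (d of 2% to 5%, f of 40% to 50%, true rate exactly 20%), false success at n=85 is about 4% to 7% against 3.3%; at d=2% it stays under the nominal 5%. A reader might infer a false-success rate of 21% or more, but that requires, for example, 10% of cases untreated with 60% incomplete. This would remove 0.06/0.20 = 30% of all failures, and nothing in the documents supports it. A true rate above 20% would shrink or cancel the effect. The better-supported argument is fragility: one uncounted incomplete case can reverse a borderline result.

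**What to change.** 1. In 8.4.1, define ITT as all enrolled patients (consented, eligible, no caecal intubation at 10 minutes) whether or not Endorail is started, counted by caecal outcome.
2. Keep the present set as a supportive Treated set and define *started*, for example as balloon guide insertion attempted.
3. In 6.2.1, replace the permissive wording with *are enrolled if no exclusion criterion is present*, which agrees with 4.4.
4. Record and tabulate every consented case over 10 minutes that was not enrolled or not started, with the reason, the time the reason was recorded and the caecal outcome.
5. Prespecify a sensitivity analysis that adds these cases by caecal outcome and compares the result with 20%.

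Item 1 covers enrolled patients who are not started. Exclusions found mid-procedure are covered only by items 4 and 5. Making all such cases primary would cost substantial power at the planned size, and enrolling them regardless of exclusions would contradict 4.4.

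The cost is one or two eCRF fields, some wording in a SAP that section 8.4 says is still to be finalised, and a slightly less favourable rate if some enrolled cases go untreated. The change does not align the baseline exclusions (BMI, ASA class, implants) with the reference population; state that as a limitation.
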